7.0 Study Objectives

7.1 Primary Objective

The primary objectives of this study are:

- To evaluate positive detection accuracy (PDA) for the D-Tect Patch.
- To evaluate detection latency measures for the D-Tect Patch.

7.2 Secondary Objective

The secondary objective of this study is to collect and characterize AEs associated with the device.

8.0 Study Design

This two-cohort, open-label, prospective trial is designed to assess the PDA and detection latency of the D-Tect Patch. The PDA is defined as the proportion of miniature ingestible event marker tablets (MITs) detected out of the total ingestible event marker (IEM) detections of tested D-Tect Patches (Cohort 1 only). For detection latency, Patch Detection Latency, Ingestion Data Transfer

| 0 |
|---|
| |
| |

Strictly Confidential. © 2023, PRA Health Sciences. All rights reserved.

Latency, and Total Detection Latency will be measured for both cohorts (i.e., MITs and Abilify MyCite).

Cohort 1 will be completed in adult, healthy subjects. Subjects with difficulty swallowing, active skin infection or history of inflammatory skin condition, or an allergy to adhesive bandages/tapes will be excluded from participation. Subjects in Cohort 1 will take the MIT dose form. A minimum of 24 healthy subjects will be tested to obtain a minimum of 360 miniature ingestible event marker tablet ingestions for Cohort 1. This trial will consist of up to 3 onsite visits including:

- Visit 1: Screening
- Visit 2 (Day 1): Testing, patch placement, directly observed ingestion (DOI) of MITs (conducted either on the same day as Visit 1 or up to 7 days after Visit 1)
- Visit 3 (Day 8): In-person safety follow-up and removal of patch (conducted approximately 7 days [+ 2 days] after applying the D-Tect Patch).

Cohort 2 will be completed in adults with serious mental illness (SMI) who are prescribed and taking aripiprazole prior to trial entry. Subjects with difficulty swallowing, active skin infection or history of inflammatory skin condition, or an allergy to adhesive bandages/tapes will be excluded from participation. Subjects will take a single dose of Abilify MyCite at the same dose as the subject's current aripiprazole prescription. Subjects will be instructed not to take their currently prescribed dose of aripiprazole at home on Day 1 of the trial when Abilify MyCite will be ingested. A minimum of 30 subjects with SMI will be tested to obtain a minimum of 30 Abilify MyCite ingestions for Cohort 2. This trial will consist of up to 3 onsite visits including:

- Visit 1: Screening
- Visit 2 (Day 1): Testing, patch placement, DOI of a single dose of Abilify MyCite (conducted either on the same day as Visit 1 or up to 7 days after Visit 1)
- Visit 3 (Day 8): In-person safety follow-up and patch removal (approximately 7 days [+ 2 days] after applying the D-Tect Patch)

No trial procedures may be conducted prior to the signing of the informed consent form (ICF), which will occur at Visit 1. Visit 2 involves patch application and DOI(s). Visits 1 and 2 may be combined and conducted on the same day. Subjects will return to the site on Day 8 (+ 2 days), 7 days following patch placement for a safety follow-up evaluation and to make final observations of patch wear (Visit 3). Any patches that remain on the subject will be removed at this visit. Any patch that falls off prior to the safety follow-up visit should be retained by the subject and given to trial staff at the scheduled follow-up visit. A full Schedule of Assessments is included in Table 1.

| Period | Screening | Testing | Follow-up |
|------------------|-----------------|----------------------|------------------------|
| Visit | Visit 1 | Visit 2 ^a | Visit 3 ^{b,c} |
| Trial Day | Day –7 to Day 1 | Day 1 | Day 8 (+2 days) |
| Informed Consent | Х | | |

Table 1: Schedule of Assessments (Cohorts 1 and 2)

Page 6 of 20

Strictly Confidential. © 2023, PRA Health Sciences. All rights reserved.

Statistical Analysis Plan (SAP) Version Date: 22-JUN-2023 Sponsor: Otsuka Pharmaceutical Development & Commercialization, Inc. Protocol No: 031-201-00521

| Demographics | Х | | |
|--|---|---|---|
| Medical History | Х | | |
| Concomitant Medications | Х | Х | Х |
| Eligibility Criteria Review | Х | | |
| Vital Sign Measurements ^d | Х | | |
| Preparation of application site and patch placement | | X | |
| Assessment of AEs ^e | Х | Х | Х |
| Photograph of patches at application site ^f | | X | Х |
| DOI ^{g,h} | | Х | |
| Sleep Diary ⁱ | | X | |
| Patch Removal ^j | | | Х |
| Pregnancy Test ^k | Х | | |

Abbreviations:

 \overline{AE} = adverse event; DOI = directly observed ingestion.

Footnotes:

^a Conducted either on the same day as Visit 1, or up to 7 days after Visit 1.

^b In-person safety follow-up to occur 7 days after applying the patch.

^c If an in-person follow-up visit cannot occur due to COVID-19 restrictions, the site should conduct a follow-up visit via video conference to verbally assess subject safety and instruct the subject to remove the patch on Day 8.

^d Vital sign measurements include blood pressure, heart rate, temperature, height, and weight.

^e If an AE is related to the patch, then the Skin Irritation Scoring System (Table 8.6.1-1) will be completed by the investigator.

^f A minimum of 3 patch placement photos are required: prior to initial dose, after completion of DOI(s), and when the subject returns for follow-up (prior to patch removal).

^g Cohort 1: Subjects will ingest 15 miniature ingestible event marker tablets (MITs) over the course of 1 visit day (with approximately 15 [-5 / +15] minutes between ingestions).

^h Cohort 2: Subjects will ingest a single dose of Abilify MyCite at the same dose as their currently prescribed aripiprazole.

ⁱ On Day 1 of the trial, subjects will be sent home with a sleep diary to complete each day until they return for the follow-up visit on Day 8 [+ 2 days].

^j Any patch that falls off during the trial should be retained by the subject and given to trial staff during the in-person follow-up visit. All patches must be removed on Day 8, even if the clinic visit is delayed.

^k To be collected from woman of childbearing potential via urine dipstick.

8.1 Sample Size Considerations

The study is exploratory in nature, the sample size is not determined based on a specific hypothesis or effect size.

For Cohort 1, a minimum of 24 subjects are planned to complete 15 DOIs per subject. With this assumption, 24 subjects with 360 ingestions will provide sufficient power to ensure the lower bound of the 95% confidence interval (CI) for PDA is at 95% assuming the PDA rate of 97.3% of the D-Tect Patch using binomial distribution.

CCI

Strictly Confidential. © 2023, PRA Health Sciences. All rights reserved.

For Cohort 2, there is no formal sample size calculation. A minimum of 30 subjects are planned to complete a single DOI of Abilify MyCite.

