| Cohort 1 | MIT (placebo embedded with | The MIT formulation is an IEM inside an inert tablet which |
| | an IEM) | will be dispensed to subjects to be ingested 15 times in |
| | | 1 day during the trial. |
| Cohort 2 | Abilify MyCite tablet | The Abilify MyCite formulation is an IEM inside an |
| | (aripiprazole embedded with | aripiprazole tablet which will be dispensed to subjects to be |
| | an IEM) | ingested one time during the trial. |
| Cohorts | D-Tect Patch | A D-Tect Patch will be applied by clinic staff prior to |
| 1 and 2 | | DOIs. |
| Cohorts | Computerized Device and | A computerized device (eg, smart phone) and accessories |
| 1 and 2 | Accessories | will be used by the clinic staff to track IEM detection on the |
| | | software application. |

DOI = directly observed ingestion; IEM = ingestible event marker; MIT = miniature ingestible event marker tablet.

Trial Assessments:

Assessments will include photographs of patches at application site, DOIs, Sleep Diary, and the Skin Irritation Scoring System (when applicable).

Independent Data Monitoring Committee: No

Statistical Methods:

The number of positive detection and PDA will be summarized for the D-Tect Patch for Cohort 1; the 95% confidence interval of PDA will be provided using the Clopper-Pearson method. A minimum of 24 subjects are planned to complete 15 DOIs per subject for Cohort 1. This will provide sufficient power to ensure the lower bound of the 95% confidence interval for PDA is at 95%, assuming the PDA rate of 97.3% of the D-Tect Patch using binomial distribution.

Summary statistics will be provided for Patch Detection Latency, Ingestion Data Transfer Latency, and Total Detection Latency. Kaplan-Meier curves will be plotted for all of the latency times.

Trial Duration:

The total duration the subject is expected to be on trial is approximately 8 days and includes the following visits:

- Eligibility screening visit
- Testing Visit / Day 1 (1 day)
- Follow-up / Day 8 (1 day)

The trial start is defined as the date the first subject signs their informed consent form. Overall, the trial duration, from signing of the first subject's informed consent form to the last subject's final assessment, is expected to be approximately 24 days.

Known and Potential Risks and Benefits:

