9.1 Sample Size

For Cohort 1, a minimum of 24 subjects are planned to complete 15 DOIs per subject. With this assumption, 24 subjects with 360 ingestions will provide sufficient power to ensure the lower bound of the 95% confidence interval (CI) for PDA is at 95% assuming the PDA rate of 97.3% of the D-Tect Patch using binomial distribution.

For Cohort 2, there is no formal sample size calculation. A minimum of 30 subjects are planned to complete a single DOI of Abilify MyCite.

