9.1 Endpoints

| Objectives | Endpoints |
|---|---|
| Primary | Primary endpoint for PDA |
| • Evaluate PDA and detection latency measures for the D-Tect Patch. | • Estimate PDA with the CI lower limit greater than 95% when a subject is wearing the D-Tect Patch. |
| | Primary endpoint for Detection Latency |
| | • The mean and median for three latency measures: Patch Detection Latency, Ingestion Data Transfer Latency, and Total Detection Latency (See Section 10.7 for detailed definition). |
| Secondary | Safety |
| • To collect and characterize AEs associated with the device. | • The frequency and severity of AEs, device- related AEs, serious AEs (SAEs), and AEs leading to discontinuation |

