12.5.1 Positive Detection Accuracy

For **FAS-Cohort 1**, the number of positive detections, the positive detection accuracy (PDA) and 95% Clopper-Pearson confidence interval (CI) will be summarized, for overall DOIs only.

Positive detections will not be reported in CRF and will rather be downloaded from the trial mobile device(s). All positive detections data will be listed together with directly observed ingestion data (Section 12.3.1) based on FAS-Cohort 1.

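### The sample-size statement claims enough power to secure a lower limit of 95%, but at the assumed PDA of 97.3% the chance of meeting the criterion with 360 ingestions is 49%.

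*SAP*

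**What the plan says.** The sample-size basis for Cohort 1 appears three times in almost the same words.

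- SAP 8.1: "For Cohort 1, a minimum of 24 subjects are planned to complete 15 DOIs per subject". It continues that "24 subjects with 360 ingestions will provide sufficient power to ensure the lower bound of the 95% confidence interval (CI) for PDA is at 95"%, and the assumption is given as "is at 95% assuming the PDA rate of 97.3% of the D-Tect Patch using binomial distribution".
- Protocol 9.1 repeats that the 360 ingestions "will provide sufficient power to ensure the lower bound of the 95% confidence interval (CI) for PDA is at 95"%.
- Protocol 1.1 (Synopsis, Statistical Methods): "This will provide sufficient power to ensure the lower bound of the 95% confidence interval for PDA is at 95"%.

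Neither document gives a power percentage or a target power.

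The primary PDA endpoint in SAP 9.1 is "Estimate PDA with the CI lower limit greater than 95% when a subject is wearing the D-Tect Patch". Protocol 1.1 and Table 3-1 set the same threshold. For the analysis, SAP 12.5.1 says that "the positive detection accuracy (PDA) and 95% Clopper-Pearson confidence interval (CI) will be summarized, for overall DOIs only", and Protocol 9.4.1 names the same method.

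The paragraph of SAP 8.1 just before the power claim says: "The study is exploratory in nature, the sample size is not determined based on a specific hypothesis or effect size".

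**The concern.** The assumed PDA lies only 2.3 percentage points above the threshold (97.3 − 95.0). With 360 ingestions, the lower arm of a 95% interval is about that wide. When the margin equals the half-width, the limit clears the threshold only if the observed rate is at or above its expected value, which happens about half the time. Choosing n this way controls precision. It does not give power, and it does not make the result assured.

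This is the only sample-size justification for the only endpoint with a numerical criterion. A reader told that the design secures the bound may take a lower limit below 95% as evidence against the patch. At the assumed PDA, a miss is about as likely as a pass. SAP 8.1 also contradicts itself: it denies any hypothesis and then claims power against a 95% threshold.

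**Working it through.** **Inputs**

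| Input | Value | Source |
|---|---|---|
| Ingestions | 24 × 15 = 360 | SAP 8.1, Protocol 9.1 |
| Assumed true PDA | 97.3%, binomial | SAP 8.1, Protocol 9.1 |
| Criterion | lower limit above 95% | SAP 9.1, Protocol Table 3-1 |
| Interval | 95% Clopper-Pearson, read as two-sided | SAP 12.5.1, Protocol 9.4.1 |

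The Clopper-Pearson lower limit for k detections in n ingestions is the 2.5% quantile of a Beta(k, n − k + 1) distribution.

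**Step 1. Reproduce the plan's figure.** Suppose the observed rate is exactly 97.3%.

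- n = 345 (23 subjects): lower limit 94.99%.
- n = 360 (24 subjects): k = 0.973 × 360 = 350.28 (not an integer), lower limit 95.05%.

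So 24 is the smallest number of subjects, at 15 ingestions each, for which the limit reaches 95%. The figure of 24 subjects and 360 ingestions reproduces as a precision calculation. The documents show no derivation, so this origin is an inference. Nothing below depends on it.

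**Step 2. Find the cut-off at n = 360.**

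- k = 350 (97.22%): lower limit 94.95%, criterion missed.
- k = 351 (97.50%): lower limit 95.31%, criterion met.

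At least 351 detections are needed. The expected number at 97.3% is 350.3.

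**Step 3. Probability of meeting the criterion.** This is P(X ≥ 351) with X ~ Binomial(360, p).

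| True PDA | Probability |
|---|---|
| 97.0% | 36.0% |
| 97.3% (assumed) | 49.2% |
| 97.5% | 58.7% |
| 98.0% | 81.2% |
| 98.5% | 95.3% |

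The documents set no target power. Taking 80% and 90% as illustrations, the true PDA would have to be about 97.97% and 98.27%.

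**Step 4. Other readings at 97.3% and n = 360.**

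| Reading | Cut-off | Probability |
|---|---|---|
| Two-sided Wilson or Agresti-Coull | 351 | 49.2% |
| One-sided 95% Clopper-Pearson | 350 | 61.9% |
| Two-sided Clopper-Pearson limit that rounds to 95.0% | 350 | 61.9% |
| Two-sided Wald | 349 | 73.0% |
| One-sided Wald | 348 | 82.0% |

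A one-sided normal approximation using the variance at 97.3% gives 85.3%. Of the readings tried, only these one-sided Wald-type calculations exceed 80%, and neither document specifies them.

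**Step 5. Other values of n at 97.3%, two-sided Clopper-Pearson.**

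| n | Cut-off | Probability |
|---|---|---|
| 345 | 336 | 54.5% |
| 355 | 346 | 51.0% |
| 358 | 349 | 49.9% |
| 360 | 351 | 49.2% |
| 375 | 365 | 56.7% |
| 390 | 379 | 63.6% |
| 450 | 437 | 66.7% |
| 600 | 581 | 80.1% |

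The probability moves in a saw-tooth because the cut-off is an integer.

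**Step 6. Clustering.** Each subject contributes 15 ingestions. In a beta-binomial simulation with assumed within-subject correlations of 0.02, 0.05 and 0.10, the probability of at least 351 detections was 50.1%, 51.5% and 52.9%.

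**The case against.** The strongest reply is that no stated number is wrong. The plan gives no power percentage, and its one derivable figure reproduces as a precision calculation. The sample-size sentence puts the limit at 95%, not above it, which suits that reading. SAP 8.1 and 9.0 call the study exploratory. No hypothesis test, decision rule or action on missing 95% is specified, and the reported PDA and interval would be the same whatever this sentence says. Finally, 360 is a minimum, and Protocol section 8 allows extra enrolment to replace missing ingestions.

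Part of this stands. The error is in what the calculation is said to show, not in the 360 itself. The documents contain no rule that would turn a miss into a declared failure, so misreading is a risk and not a certainty. The cut-off of 351 applies only if exactly 360 ingestions are evaluable, and SAP 9.2.3 and 10.6 exclude malfunction sessions from the denominator.

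The reply does not rescue the sentence. A limit that merely rounds to 95.0% is reached only 62% of the time. Even 450 ingestions give 67%. The exploratory label appears only in the SAP, where it conflicts with the power claim beside it; both protocol statements make the claim without that label. Protocol 4.2 says the trial is meant to demonstrate performance comparable with predecessor patches, so a reader has reason to treat the 95% limit as a target.

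**Conclusion.** The statement is wrong as written in SAP 8.1 and in Protocol 1.1 and 9.1. With the documents' own sample size, assumed PDA, interval method and criterion, the probability that the lower limit exceeds 95% is 49.2%. That cannot be described as sufficient power, still less as ensuring the result.

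The figure assumes 360 evaluable and independent ingestions, a true PDA of exactly 97.3%, and a two-sided interval. The conclusion holds under plausible changes to the evaluable number and under modest clustering. It changes only if the true PDA is higher than assumed, at about 98% or more, or if the interval is replaced by a one-sided Wald-type approximation that the plan does not use.

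**What to change.** Replace the sentence in Protocol 1.1, Protocol 9.1 and SAP 8.1 with text such as:

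> If all 360 ingestions are evaluable, the lower limit of the two-sided 95% Clopper-Pearson interval for PDA exceeds 95% when at least 351 are detected. Assuming independent ingestions, the probability of this is 49% if the true PDA is 97.3%, 81% if it is 98.0% and 95% if it is 98.5%.

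Remove the power claim altogether. Then settle the conflict within SAP 8.1 in one of two ways:

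- keep the 95% criterion as a target and delete the sentence saying the size rests on no specific hypothesis; or
- say that 360 was chosen for precision, and that missing the criterion is not in itself evidence of a PDA below 95%.

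The cost is a wording change in three places and a less favourable stated figure. No extra subjects are needed, and conduct, data collection and analysis do not change. For context only, if the sponsor did want 80% probability at 97.3%, about 600 ingestions (40 subjects × 15) would be needed.

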8.2 Randomization

Randomization is not applicable to this study.

9.0 Study Estimands

The 'Estimands' framework is used to define the treatment effect of interest in a clinical trial, which specifies how the treatment effect is to be estimated, and what assumptions are necessary to make the estimation valid. In this study, the treatment effect, as well as the potential sources of bias or variability that may impact the estimation of treatment effects, are not the research question of interest. The objective of this study is to assess the PDA and detection latency of the D-Tect Patch in an exploratory manner, therefore, the estimands in this study are not applicable.

9.1 Endpoints

| Objectives | Endpoints |
|---|---|
| Primary | Primary endpoint for PDA |
| • Evaluate PDA and detection latency measures for the D-Tect Patch. | • Estimate PDA with the CI lower limit greater than 95% when a subject is wearing the D-Tect Patch. |
| | Primary endpoint for Detection Latency |
| | • The mean and median for three latency measures: Patch Detection Latency, Ingestion Data Transfer Latency, and Total Detection Latency (See Section 10.7 for detailed definition). |
| Secondary | Safety |
| • To collect and characterize AEs associated with the device. | • The frequency and severity of AEs, device- related AEs, serious AEs (SAEs), and AEs leading to discontinuation |

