2.3.3 COVID-19 Management Plan

The clinical research site is expected to adhere to all United States Center for Disease Control (CDC), state, and local coronavirus disease 2019 (COVID-19) guidelines.

| Table 3-1Trial Objectives and Endpoints | | | |
|--|--|--|--|
| Objectives | Endpoints | | |
| Primary: Evaluate PDA and detection latency measures for the D-Tect Patch. | PDA: Estimate PDA with the CI lower limit greater than 95% when a subject is wearing the D-Tect Patch. | | |
| | Detection Latency: The median Patch Detection Latency, Ingestion Data Transfer Latency, and Total Detection Latency. See Section 2 for the definition of the detection latency metrics. | | |
| Secondary: | Safety: The frequency and severity of AEs, | | |
| • To collect and characterize AEs associated with the device. | device-related AEs, serious AEs (SAEs), AEs leading to discontinuation, and unanticipated adverse device effects. | | |

3 **Objectives and Endpoints**

AE = adverse event; CI = confidence interval; PDA = Positive Detection Accuracy; SAE = serious adverse event.

Section 9.4 describes the statistical analysis of the endpoints.

Confidential - Proprietary Information

Approval: 18 Apr 2023

Until the information herein is released by Otsuka to the public domain, the contents of this document are Otsuka confidential information and should not be duplicated or re-distributed without prior written consent of Otsuka.

4 Trial Design

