9.3 Handling of Missing Data for Primary and Secondary Endpoint Analysis

Missing data on PDA and/or detection latency measures will not be imputed.

9.4 **Statistical Analyses**

9.4.1 **Primary Endpoints**

The number of positive detections and PDA will be summarized for the D-Tect Patch for Cohort 1; the 95% CI of PDA will be provided using the Clopper-Pearson method. PDA is defined as PDA = $k \div n$, where n is the number of the total DOIs, and k is the number of positive detections by the patch.

For detection latency, summary statistics will be provided for Patch Detection Latency, Ingestion Data Transfer Latency, and Total Detection Latency. Kaplan-Meier curves will be plotted for all of the latency times.

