6.1 Changes from Protocol

There are no major discrepancies between protocol and SAP, only the following minor differences are described:

- 1. Population definitions (SCR, FAS, FAS-Cohort 1, and FAS-Cohort 2) added, the protocol specified the intent-to-treat population, however, the full analysis set will be used.
- 2. The unanticipated adverse device effects stated in the protocol removed from the analysis.
- 3. AEs leading to discontinuation of the investigational device removed from analysis, instead AEs leading to study discontinuation will be analyzed.

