10.7 Definition of Detection Latency

As shown in the system diagram in Figure 1, there are 4 time-stamped events (TSEs) associated with measuring detection latency shown in Table 3.

Table 3: Time-stamped events (TSEs) associated with measuring detection latency

| TSE 1 | Subject takes tablet. Directly observed ingestion time is recorded by the clinician. |
|-------|--|
| TSE 2 | Tablet sends signal to the patch. Tablet is detected & recorded by the patch as an IEM record with a timestamp. |
| TSE 3 | Patch sends ingestion data to phone. The tablet ingestion data is communicated to and recorded by the mobile device as a pill-ingestion-metric with a timestamp. |
| TSE 4 | Tablet ingestion data is displayed. The tablet display event is triggered on the mobile device as a pill-display-event with a timestamp. |

Figure 1: Digital Medicine System

The latency measurements between each of above timestamps are defined in Table 4.

Table 4. Latency measurements

| Table 4. Datency m | casul cilicitis | |
|--------------------|-----------------|---------------|
| CCI | | Page 11 of 20 |
| | | Page 11 of 20 |

Strictly Confidential. © 2023, PRA Health Sciences. All rights reserved.

Statistical Analysis Plan (SAP) Version Date: 22-JUN-2023 Sponsor: Otsuka Pharmaceutical Development & Commercialization, Inc. Protocol No: 031-201-00521

| Latency Measurements | Definition | Maximum Observation Time |
|---------------------------------|---|-----------------------------|
| Patch Detection Latency | Time between TSE 1 and TSE 2 in seconds | 10 minutes/600 seconds |
| Ingestion Data Transfer Latency | Time between TSE 2 and TSE 4 in seconds | 5 minutes/300 seconds |
| Total Detection Latency | Time between TSE 1 and TSE 4 in seconds | 15 minutes/900 seconds |

For Kaplan-Meier estimate, if the DOI is successfully detected, it will be treated as positive detection and event = "1"; If the DOI is not successfully detected or latencies have been larger than the maximum observation time (defined above in Table 4), the data will be considered as censored data and event = "0", where time to event is defined as maximum observation time.

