10.8 Missing Data

All statistical analysis will be based on observed values. Missing values will not be imputed.

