12.0 Statistical Methods

All analyses will use SAS® version 9.4 or higher. Table and listing outputs will be presented using ICON standard layouts.

Unless specified otherwise, categorical variables will be summarized using counts and percentages (n [%]). Percentages will be rounded to one decimal place, except 100% will be displayed without any decimal places and percentages will not be displayed for zero counts.

Continuous variables will be summarized using the number of observations (n), mean, and standard deviation, median, minimum, and maximum. The minimum, and maximum values will be displayed to the same level of precision as the raw data; the mean and the median to a further decimal place; and the standard deviation to two additional decimal places to a maximum of four.

In listings, data will be presented with the same precision as the original data.

Unless specified otherwise, all the tables will be produced by cohort, and overall will not be displayed.

Unscheduled visits will not be summarized or included in any analysis but will be included in listings outputs.

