12.5.2 Detection Latency Measures

As defined in **Table 3**, the directly observed ingestion time (TSE 1) is recorded in the CRF. Other signal detection times (TSE 2-4) will be downloaded from the trial mobile device(s) for analysis. The derivation of detection latency measures, including Patch Detection Latency, Ingestion Data Transfer Latency, and Total Detection Latency, are provided in **Table 4**.

The three detection latency measures for all DOIs will be summarized using descriptive statistics, for **FAS-Cohort 1** and **FAS-Cohort 2** separately.

Furthermore, two Kaplan-Meier curves will be plotted for all of the latency times (all DOIs), for **FAS-Cohort 1** and **FAS-Cohort 2** separately. The three detection latency measures will be displayed as three curves on the plot. A table will be provided to show the summary of survival status, the median (50% survival time), and 25% and 75% percentiles of survival by Kaplan-Meier estimate.

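### SAP 9.1 adds the mean to the primary latency endpoint without declaring it, gives no rule for missed or late tablets in that mean, and does not say which of two medians is the endpoint

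*SAP*

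**What the plan says.** **Endpoint.** Protocol Table 3-1, like the synopsis, gives the primary latency endpoint as "The median Patch Detection Latency, Ingestion Data Transfer Latency, and Total Detection Latency". SAP 9.1 gives "The mean and median for three latency measures: Patch Detection Latency, Ingestion Data Transfer Latency, and Total Detection Latency". SAP 6.1 states "There are no major discrepancies between protocol and SAP, only the following minor differences are described" and lists three items: the analysis populations, unanticipated adverse device effects, and AEs leading to discontinuation of the device. None concerns latency.

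**How the mean is obtained.** SAP 12.5.2: "The three detection latency measures for all DOIs will be summarized using descriptive statistics", separately by cohort. SAP 12.0 defines the content: "Continuous variables will be summarized using the number of observations (n), mean, and standard deviation, median, minimum, and maximum". SAP 10.8 bases every analysis on observed values and adds "Missing values will not be imputed". Protocol 9.3 likewise rules out imputing latency.

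**How misses and late values are handled.** SAP 10.7, Table 4, gives a maximum observation time for each measure: 600 s for Patch Detection Latency, 300 s for Ingestion Data Transfer Latency and 900 s for Total Detection Latency. The sentence that applies these limits is introduced as a rule for the Kaplan-Meier estimate. It codes an undetected or over-limit ingestion as censored, "where time to event is defined as maximum observation time".

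**Medians.** SAP 12.0 produces a descriptive median. SAP 12.5.2 also plans a Kaplan-Meier median with quartiles. SAP 9.1 points to 10.7 for definitions, but 10.7 does not say which median is the endpoint.

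**The concern.** A statistic has been raised to primary rank in the SAP, and the section meant to record such changes does not record it. That statistic is also the one most exposed to the two awkward kinds of observation in this trial.

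- **Missed tablets.** An undetected tablet has no patch or display timestamp, so it has no latency and falls outside the mean, although SAP 12.5.2 speaks of all DOIs. If the tablets that are missed would have been slow ones, the mean gets shorter as detection gets worse.
- **Late values.** A mean without an upper limit can be moved by a single long transfer, especially with 30 ingestions in Cohort 2.

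The same ingestion can therefore be treated in two ways within one primary analysis: censored at the limit in the Kaplan-Meier table, and absent from or at full size in the descriptive table. With two medians and no named endpoint, the choice between summaries would be left until the results are known.

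**Working it through.** The documents state no target, standard deviation, power or expected value for latency, so there is no plan figure to reproduce. What follows is arithmetic on stated counts and assumed latencies.

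**Inputs from the documents**
- Cohort 1: 360 ingestions, assumed detection rate 97.3% (Protocol 9.1). Expected misses: 360 × 0.027 = 9.7, about 10, leaving 350 detected.
- Cohort 2: 30 ingestions (Protocol 9.1). At the same rate, 30 × 0.027 = 0.8, about 1 miss.
- Limits of 600, 300 and 900 s (SAP Table 4).

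**Assumptions:** mean patch latency *b* among detected tablets of 60, 120 or 180 s; typical transfer latency of 30 s; one transfer delayed by 3,600 s; no ingestions removed from the analysis set.

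**Step 1: misses.** With misses left out, the mean is *b*. With *m* of *N* misses counted at 600 s, it is ((*N* − *m*)*b* + 600*m*)/*N*. The difference is (*m*/*N*)(600 − *b*).

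| Assumed *b* (s) | Cohort 1, 10 of 360: mean with misses at 600 s | Difference (s) | Cohort 2, 1 of 30: mean with misses at 600 s | Difference (s) |
|---|---|---|---|---|
| 60 | 75.0 | 15.0 | 78.0 | 18.0 |
| 120 | 133.3 | 13.3 | 136.0 | 16.0 |
| 180 | 191.7 | 11.7 | 194.0 | 14.0 |

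**Step 2: one late transfer.** The mean is ((*N* − 1) × 30 + *D*)/*N*, with *D* = 3,600 s, or 300 s if the limit is applied.
- Cohort 1 (350 detected): (349 × 30 + 3,600)/350 = 40.2 s; with the limit, 30.8 s. The late value adds (3,600 − 30)/350 = 10.2 s to a 30 s mean and makes up 3,600/14,070 = 26% of the total.
- Cohort 2 (30 detected): (29 × 30 + 3,600)/30 = 149.0 s; with the limit, 39.0 s. The late value adds (3,600 − 30)/30 = 119 s and makes up 3,600/4,470 = 81% of the total.

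**Step 3: the median.** Because misses are censored at the limit, the Kaplan-Meier median is the time by which half of all ingestions are detected. That is the 0.5/0.973 = 51.4th percentile of the detected latencies. In a simulated lognormal example with median 90 s and log-scale SD 0.6, the detected-only median is 89.9 s and the Kaplan-Meier median 91.8 s.

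**Step 4: the transfer measure.** Transfer latency starts when the patch detects the tablet. The 10.7 rule as worded also censors undetected tablets at 300 s on this curve. With 10 misses in 360, the curve could show at most 350/360 = 97.2% transferred even if every transfer were immediate. A Kaplan-Meier median for this measure therefore needs its own denominator.

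**The case against.** The strongest reply is that little changes in substance. The median remains in the SAP endpoint. Protocol 9.4.1 already promises "For detection latency, summary statistics will be provided for Patch Detection Latency, Ingestion Data Transfer Latency, and Total Detection Latency", so a mean would have been reported in any case. The SAP calls the study exploratory. Latency has no threshold, test or error rate. The SAP also plans n, the maximum and a summary of survival status, and in Cohort 1 the latency results share a table with positive detections. A careful reader could therefore see misses and outliers, and PDA measures Cohort 1 misses directly. All of this stands, and it limits the point to how the primary estimate is defined and labelled. It does not explain why the mean became primary without an entry in 6.1, or which median is the endpoint.

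Some stronger readings are tempting but not supported:

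- *The SAP replaced the median, or a trial conclusion turns on this.* The mean was added beside the median, and no decision rule uses latency.
- *The SAP says the mean is uncapped.* It does not say so. The limits sit in the table of latency definitions, and only the rule applying them is confined to Kaplan-Meier. An unlimited mean is the natural reading, but it is an inference.
- *One late transfer will dominate.* No latency data are given, and staff follow detections on the app during testing. With one hour and a 30 s typical value, domination appears in Cohort 2 but not in Cohort 1.
- *A Bluetooth delay has nothing to do with the patch.* Protocol Section 2 places the Bluetooth interface within the wearable sensor.
- *The protocol specified a Kaplan-Meier median.* It names only a median, with Kaplan-Meier curves to be plotted. Naming the Kaplan-Meier median is a new specification.
- *The two medians would differ materially.* In the example they differ by about 2 s, while ingestion time is recorded to the nearest minute (Protocol 8.10.2).

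**Conclusion.** The point holds in a limited form and should be corrected before analysis. The SAP raises the mean to a primary latency endpoint without declaring it. It gives that mean no rule for undetected or over-limit ingestions, and it leaves the primary median ambiguous. The consequence falls on the reported primary estimate and on no pass/fail result.

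On the assumed latencies, leaving out misses shortens the patch-latency mean by about 12 to 15 s in Cohort 1 and, with one miss, by about 14 to 18 s in Cohort 2. A single 1-hour transfer would lengthen the mean transfer latency by about 10 s and about 120 s respectively. The median barely moves in either case. These sizes depend on assumed latencies and on an assumed delay, neither of which the documents supply. The undeclared addition and the unnamed median do not depend on any assumption.

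**What to change.** 1. In SAP 9.1, make the median the only primary latency endpoint, as in the protocol.
2. Specify the Kaplan-Meier median for Patch Detection Latency and Total Detection Latency, with misses and over-limit values censored at the Table 4 limit as 10.7 already provides.
3. For Ingestion Data Transfer Latency, specify the Kaplan-Meier median among ingestions that the patch detected (those with a TSE 2 timestamp). Censor at 300 s only for a late or failed transfer, and amend 10.7 to match.
4. Report the mean as supportive, headed as applying to ingestions with an observed latency, with the number missed and the number beyond the Table 4 limit beside it.
5. If the mean is to stay primary, declare it in SAP 6.1 and use the mean restricted to the Table 4 limit.

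The cost is SAP wording, a table header and two counts, plus a changed denominator for the transfer curve. The Kaplan-Meier medians and quartiles are already planned, and no new data are needed.
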